3.6. Determination of Sample Size

[figure not shown]
The sample size calculation is based on the effect size that was observed for the primary endpoint (change from baseline in MAS in the SMG) from the registration study of Dysport ([Gracies J. 2015](#)) for the treatment of ULS. With a mean change from baseline in MAS in the SMG difference between an active treatment and the placebo arm of 0.9 to 1.1 and a common standard deviation of 1.1, the minimum effect size (Cohen's d) targeted is 0.8 to 1.0.

[figure not shown]
This document is confidential.

This document is confidential.

This document is confidential.

This document is confidential.

4. Endpoints

4.1. Co-Primary Endpoints

The co-primary endpoints of this study are:

- Mean change from baseline in muscle tone measure with the MAS in the SMG of the elbow, wrist, OR finger flexors at Week 6
- Mean score of the PGIC at Week 6

This document is confidential.

This document is confidential.

5. Analysis Populations

5.1. Screened Population

The Screened Population will include all subjects screened for entry into the study. This population will be used for disposition summaries and listings.

5.2. Randomized Population

[figure not shown]
The Randomized Population will include all subjects randomized into the study. This population will be used for protocol deviation summaries and all listings.

5.3. Safety Population

The safety population is defined as all randomized subjects who received Investigational product. The safety population will be analyzed by treatment arm as treated (i.e., based on the treatment the subject actually received rather than the treatment to which the subject was randomized). The safety population will be used to for all safety analyses.

5.4. Intent-to-Treat Population

The Intent-to-Treat (ITT) population is defined as all subjects who were randomized, received study injections in this study, and have a MAS score in the SMG at baseline and at least one post-baseline assessment. This population will be used for all efficacy analyses. The ITT population will be classified by treatment arm as randomized (i.e., treatment arm will be based on randomization assignment).

5.6. Pre-COVID-19 ITT Population

The Pre-COVID-19 ITT population will be a subset of the ITT population and includes subjects who were enrolled before the COVID-19 enrollment hold on 20-March-2020. This population will be classified by treatment arm as randomized.

5.7. Pre-COVID-19 PP Population

The Pre-COVID-19 PP population will be a subset of the PP population and includes subjects who were enrolled before the COVID-19 enrollment hold on 20-March-2020. This population will be classified by treatment arm as randomized.

5.8. Protocol Deviations

Protocol deviations will be summarized for all randomized subjects by treatment arm and total. A listing will be provided for all protocol deviations. A separate summary table and listing will be provided for any protocol

This document is confidential.

deviations related to COVID-19. The summary of Covid-19 related PDs will include number of subjects impacted, as well as missed visits, missed assessments, remote visits, and remote assessments.

6. General Aspects for Statistical Analysis

6.1. General Methods

- Unless otherwise specified, summaries will be presented for each treatment group.
- Continuous variables will be summarized using the number of observations (n), mean, standard deviation (SD), median, minimum, and maximum. Categorical variables will be summarized using number of observations (n), frequency and percentages of subjects.
- All relevant subject data will be included in listings. All subjects entered into the database will be included in subject data listings.
- Unless otherwise specified, if a subject has more than one observation at a given time point, the value closest to the target day for that visit will be used. If two observations are equal distance from the target day, the later observation will be used.
- All analyses and outputs will be generated using SAS® or SAS/IML® version 9.4 or higher.

[figure not shown]
6.2. Key Definitions

Study day will be assigned as follows:

- Before the study medication dose date, study day = visit date – dose date.
- After the study medication dose date, study day = visit date – dose date + 1.

The day the study medication is given will be Day 1, and the day before the study medication is given will be considered Day -1.

[figure not shown]
Unless otherwise specified, baseline is defined as the last non-missing value before the dose of study medication. Change from baseline is defined as the post-baseline value minus the baseline value (post-baseline – baseline). Percent change from baseline is defined as 100 times (post-baseline value minus baseline value) divided by the baseline value (100*(post-baseline-baseline)/baseline).

This document is confidential.

6.4. Visit Windows and Remapping of End of Study Visit

Analyses will be based on the visit designation. Visits are required to be within specified time windows relative to the Day 1 or Baseline visit.

This document is confidential.

6.5. Pooling of Centers

Treatment centers with less than 4 subjects will be considered for pooling. Pooling will be based on geographic proximity. No pooled center will contain more than 20 randomized subjects. Final pooling of centers will be determined prior to database lock.

7. Demographic, Other Baseline Characteristics and Medication

[figure not shown]
7.1. Subject Disposition and Withdrawals

The number and percentage of subjects screened, randomized, completed, and discontinued will be summarized along with the reasons for discontinuation. The number of subjects in each study population will also be presented. Listings will be provided for disposition data, study populations and reasons for exclusion from the study population, and inclusion/exclusion criteria not met.

A summary of the duration of the subject participation in the study will be produced, including the n, mean, SD, median, minimum, and maximum duration in weeks, as well as the number and percentage of subjects in the following categories of duration: <4 weeks, 4 to < 6 weeks, 6 to <12 weeks, 12 to <24 weeks, and 24 to 36 weeks. If a subject is lost to follow-up, their participation in the study will be calculated based on their date of last visit.

7.2. Demographic and Other Baseline Characteristics

Demographic and baseline characteristics will be summarized for the ITT, Pre-COVID-19 ITT, PP, Pre-COVID-19 PP, and safety populations.

[figure not shown]

7.3. Medical History and Concomitant Diseases

Medical history and concomitant diseases will be coded according to Medical Dictionary for Regulatory Activities (MedDRA) version 22.0 or higher. A summary of medical history and concomitant diseases for the safety population by system organ class and preferred term. Terms in the table will be sorted alphabetically. A listing will also be provided that includes the system organ class, preferred term, and verbatim term for each medical history and concomitant disease. The listing will be sorted by treatment group, subject, system organ class, preferred term, and verbatim term.

7.4. Other Baseline Characteristics

Summaries will also be provided for the ITT, Pre-COVID-19 ITT, PP, Pre-COVID-19 PP, and safety populations for ULS history.

This document is confidential.

7.5. Medication

Prior and concomitant medication will be coded using World Health Organization Drug Dictionary (WHODD) version March 2018 or higher. Anatomic Therapeutic Chemical (ATC) level 2 and preferred names will be included in all summaries and listings. Listings will also include verbatim terms. Summary tables will be presented in alphabetical order, and listings will be presented for each subject by earliest start date and then alphabetical order. The listing will indicate if the medication was prior or concomitant. Prior medications for ULS will be summarized and listed separately. Summaries will be provided for the safety population.

7.5.1. Prior Medication

Medications that were stopped before the study medication dose date will be classified as prior. A summary table will be provided for prior medications.

7.5.2. Concomitant Medication

Medications that were taken on or after the study medication dose date will be classified as concomitant. This classification includes medications that were started after the study medication dose date or medications that began before and continued to be taken after the study medication dose date.

8. Efficacy

All efficacy analyses will be performed for the ITT and PP populations, with the ITT population serving as the primary analysis. Efficacy analyses with PP populations will be supportive in nature. Sensitivity analyses will also be performed on the primary and key secondary efficacy endpoints, analyses of duration of effect, and selected exploratory efficacy endpoints using the Pre-COVID-19 ITT and Pre-COVID-19 PP populations. All statistical tests will be 2-sided at the 0.05 significance level, unless otherwise indicated. All efficacy endpoints will be summarized with descriptive statistics by treatment arm and visit.

8.1. Co-Primary Efficacy Endpoints and Analyses

The co-primary efficacy endpoints are:

- Mean change from baseline in muscle tone measured using the MAS in the SMG of the elbow, wrist, OR finger flexors at Week 6
- Mean score on the Physician Global Impression of Change (PGIC) at Week 6.

The MAS measures resistance during passive soft-tissue stretching. It is a quick and easy measure that can help assess the efficacy of treatment. The following conventions prevail:

- The MAS is performed in the supine position (this will garner the most accurate and the lowest score as tension anywhere in the body will increase spasticity)
- Because spasticity is “velocity dependent” (the faster the limb is moved, the more spasticity is encountered), the MAS is performed while moving the limb at the “speed of gravity”; this is defined as the same speed at which a non-spastic limb would naturally drop (fairly fast)
- The test is performed a maximum of three times for each joint; if more than three times, the short-term effect of a stretch can influence the score
- The MAS is performed prior to goniometric testing; goniometric testing provides a stretch, and the short-term effect of a stretch can influence the score

Original MAS Scoring

This document is confidential.

0 = Normal tone, no increase in tone
1 = Slight increase in muscle tone, manifested by a catch and release or minimal resistance at the end of the range of motion (ROM) when the affected part(s) is moved in flexion or extension
1+ = Slight increase in muscle tone, manifested by a catch, followed by minimal resistance throughout the remainder (less than half) of the ROM
2 = More marked increase in muscle tone through most of the ROM, but affected part(s) easily moved
3 = Considerable increase in muscle tone, passive movement difficult
4 = Affected part(s) rigid in flexion or extension

Because the original MAS score is a categorical variable, the re-coding will be applied to be able to treat it as a continuous variable in the mean change from baseline statistical analysis. Recoding is listed in [Table 4](#). All analyses will use the recoded MAS scores.

Table 4: MAS Re-coding

Original MAS score	Derived MAS score
0	0
1	1
1+	2
2	3
3	4
4	5

The PGIC is a questionnaire that captures the physician's overall impression of the subject's response to study treatment. The physician's selected response maps to a 9-point scale: -4 (Markedly worse), 0 (about the same), to +4 (Markedly improved). The PGIC scale is presented in [Table 5](#) below.

Table 5: PGIC Questionnaire

Please choose the response that best describes the overall change in your subject's upper limb spasticity since the start of the study medication	
 -4	Markedly worse
 -3	Very much worse
 -2	Moderately worse
 -1	A little worse
 0	About the same
 +1	A little improved
 +2	Moderately improved
 +3	Very much improved

This document is confidential.

 +4	Markedly improved
-----------------------------	-------------------

8.1.1. Primary Analyses of the Co-Primary Endpoints

[figure not shown]
The primary analysis will be based on the ITT population.

The mean change from baseline in muscle tone measured using the MAS in the SMG at Week 6 between treatment arms will be compared using analysis of covariance (ANCOVA) model with baseline MAS score as covariate and terms for treatment, and the two randomization stratification factors (pooled study center, history of prior treatment with BoNT products). The 3 pairwise comparisons considered for this co-primary endpoint are:

- H111: DAXI 500 U versus placebo at week 6
- H211: DAXI 375 U versus placebo at week 6
- H311: DAXI 250 U versus placebo at week 6

The mean score on the co-primary endpoint PGIC at Week 6 will be compared between treatment arms using the analysis of covariance (ANCOVA) model with terms for treatment, and the two randomization stratification factors (pooled study center, history of prior treatment with BoNT products). The 3 pairwise comparisons considered for this co-primary endpoint are:

- H121: DAXI 500 U versus placebo at week 6
- H221: DAXI 375 U versus placebo at week 6
- H321: DAXI 250 U versus placebo at week 6

8.1.2. Sensitivity Analysis of the Co-Primary Endpoints

The primary analyses will be repeated using the PP population, the Pre-COVID-19 ITT population, and the Pre-COVID-19 PP population as supportive analyses.

The sensitivity of the primary endpoint results to missing data will be evaluated in the following additional analyses, a permutation test, and a tipping point analysis. A permutation test will be done that will fit 1000 datasets using the same ANCOVA model as the primary analysis, but with randomly assigned

This document is confidential.

pseudo-treatment group designations ([Stedman, 2009](#)). The empirical p-value will be obtained from the permutation test. This non-parametric based permutation test provides a conservative way to assess the co-primary efficacy endpoints.

[figure not shown]
A sensitivity analysis with a tipping point analysis approach will be performed to assess how severe departures from the assumption of data missing at random (MAR) must be to overturn conclusions from the primary analysis. This analysis will be performed for both co-primary efficacy endpoints. Implementing the tipping point approach will include the following steps with the first 3 steps being the standard multiple imputation steps:

1. Missing data are filled in using multiple imputation to generate 100 complete data sets as described in steps 1 and 2 in [Section 19](#).
2. The 100 complete datasets are analyzed by using the same ANCOVA model as the primary analysis.
3. The results from the 100 complete datasets are combined for inference.
4. Step 1 is repeated to generate multiple imputation datasets with a specified shift in the imputed values for observations in the treated group. No shift will be made for the placebo group.
5. Repeat step 2 for the imputed data sets with the shift parameter applied.
6. Repeat step 3 to assess statistical significance.
7. Repeat steps 4-6 with more stringent shifts until loss of statistical significance.
8. Assess whether the degree of departure from MAR needed to change the substantive results is clinically plausible. If the treatment effect is qualitatively maintained for the range of shift parameters that are considered to be clinically plausible, then the findings are considered to be robust.

[figure not shown]
The change from baseline of the MAS in SMG at all post-treatment visits will be analyzed using MMRM with fixed factors of pooled center, history of prior treatment with BoNT products, treatment arm, visit, and treatment arm by visit interaction, and the baseline MAS score as a covariate. The PGIC will be analyzed using MMRM with fixed factors of pooled center, history of prior treatment with BoNT products, treatment arm, visit, and treatment arm by visit interaction. An unstructured variance-covariance (UN) structure will be used in the model. If the model with UN structure does not converge, the autoregressive (AR1) structure will be used with the assumption that measurements that are close to each other in time are going to be more closely correlated and as measurements get farther apart in time they are less correlated.

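### With 1000 random relabelings, the permutation p-value carries a 95% Monte Carlo half-width of about 0.0135 near 0.05, so a borderline sensitivity result can depend on the seed; 10,000 or more would largely remove this

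*SAP*

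**What the plan says.** SAP 8.1.1 makes the ANCOVA the primary analysis ("The primary analysis will be based on the ITT population") and lists three dose-versus-placebo comparisons for each of the two co-primary endpoints, six in all.

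SAP 8.1.2 then adds supportive work: "The sensitivity of the primary endpoint results to missing data will be evaluated in the following additional analyses, a permutation test, and a tipping point". For the permutation test the plan is: "A permutation test will be done that will fit 1000 datasets using the same ANCOVA model as the primary analysis", each dataset having randomly assigned "pseudo-treatment group designations". Then: "The empirical p-value will be obtained from the permutation test". The section describes the test as a conservative way of assessing the co-primary endpoints.

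SAP 8.1.2 sets no cut-off for this p-value. The only level that would apply is the general one in SAP Section 8 (Efficacy): "All statistical tests will be 2-sided at the 0.05 significance level, unless otherwise indicated". The visible text gives no Monte Carlo interval, no p-value convention, no seed and no rule for a borderline result. Parts of the SAP are not visible, so some of these may be stated elsewhere.

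**The concern.** Random relabeling samples the permutation distribution and does not enumerate it. The reported p-value therefore carries simulation error in addition to whatever the data say. That error depends only on the number of relabelings and would be there under any permutation scheme or null hypothesis.

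What is at stake is how the check reads. A result far from 0.05 will read the same at any seed. A borderline one, where a robustness check is most likely to be consulted, may appear to contradict or to support the ANCOVA by chance alone. The study report would then have to explain a disagreement that says nothing about the data.

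**Working it through.** **Inputs**
- Relabelings m = 1000, randomly assigned (SAP 8.1.2).
- Level 0.05, two-sided (SAP Section 8, general default).
- Design effect, from SAP 3.6: "With a mean change from baseline in MAS in the SMG difference between an active treatment and the placebo arm of 0.9 to 1.1" with "a common standard deviation of 1.1".
- About 128 subjects (SAP 3.4). The allocation ratio is not visible, so 32 per arm (128/4) is an assumption.

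The value 1000 is a design choice, so the plan has no precision figure to reproduce. Its effect size does reproduce: 0.9/1.1 = 0.82 and 1.1/1.1 = 1.00, matching the stated 0.8 to 1.0.

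**Step 1. Monte Carlo error at p = 0.05.** The count b of relabelings at least as extreme as the observed data is Binomial(m, p), so SE = √(p(1−p)/m).
- m = 1000: √(0.05 × 0.95/1000) = 0.0069; half-width 1.96 × 0.00689 = 0.0135, that is 0.0365 to 0.0635.
- m = 10,000: SE 0.0022; half-width 0.0043.
- m = 50,000: half-width 0.0019.

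**Step 2. Chance of landing on the wrong side of 0.05 (exact binomial).** The SAP states no convention, so both are shown.

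| Exact p | m = 1000, b/m | m = 1000, (b+1)/(m+1) | m = 10,000, b/m | m = 10,000, (b+1)/(m+1) |
|---|---|---|---|---|
| 0.040 | 4.9% | 6.6% | <0.1% | <0.1% |
| 0.045 | 19.9% | 24.2% | 0.8% | 0.9% |
| 0.055 | 27.0% | 22.5% | 1.4% | 1.3% |
| 0.060 | 10.1% | 7.8% | <0.1% | <0.1% |

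With 1000 relabelings and b/m, two independent seeds give opposite answers 2 × 0.801 × 0.199 = 32% of the time at exact p = 0.045, and 2 × 0.270 × 0.730 = 39% at 0.055.

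**Step 3. Where it matters.** With 1000 relabelings and b/m, the chance of a wrong-side result is at least 2.5% only for exact p between about 0.038 and 0.065. The other convention shifts this band by about 0.001.

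**Step 4. How often that would happen.** With 32 per arm and a normal approximation, the test statistic has mean d × √(32/2) = 4d. Averaging the wrong-side chance at m = 1000 over the resulting distribution of p gives, per comparison:

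| True d | Any wrong-side result | Exact p significant, empirical p not |
|---|---|---|
| 1.00 | 0.2% | 0.1% |
| 0.82 | 0.8% | 0.4 to 0.5% |
| 0.50 | 1.9% | 0.8 to 1.0% |

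The ranges cover the two conventions. If all six comparisons had d = 0.82, the chance of at least one wrong-side result would be at most 6 × 0.8% = 4.8%. The design figures are for MAS only; the visible text gives none for PGIC.

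**The case against.** The strongest reply is that no decision depends on this p-value. The primary analysis is the ANCOVA, and the visible text gives the permutation test no part in the six-step hierarchical procedure in the protocol synopsis. It stands beside the per-protocol, pre-COVID-19, tipping-point and MMRM analyses. That is correct, and it settles the rating as minor. A reader might infer from the 20 to 27% figures that the trial's efficacy conclusion hangs on a random seed; the documents do not support that.

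Second, those percentages are conditional on an exact p already sitting at 0.045 or 0.055. Read as the overall risk they would badly overstate it; Step 4 gives the unconditional figures.

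Third, SAP 8.1.2 sets no pass or fail rule for the permutation test, so the 0.05 comparison is inferred from the general default in Section 8. This stands as a qualification. Even without a formal cut-off, a p-value near 0.05 printed without its ±0.0135 would be read as more precise than it is.

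Fourth, a seed, a convention or a borderline rule may be in text that is not visible, so it should not be claimed that the SAP lacks them. A seed would not answer the point in any case: it makes a result repeatable but leaves the error the same size.

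**Conclusion.** The point holds as a minor precision remark on a supportive analysis. With 1000 relabelings the empirical p-value is known only to within about ±0.0135 near 0.05, and an exact p of 0.045 or 0.055 would be placed on the wrong side in about one seed in four or five. The consequence is limited to whether this sensitivity check appears to agree with the ANCOVA.

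The Monte Carlo figures follow from the stated 1000 and the general 0.05 level alone. The overall chance per comparison, about 0.2 to 0.8% at the design effects and about 2% at d = 0.5, also rests on the assumed 32 per arm and the normal approximation. The change is worth making because it costs so little, not because the risk is large.

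**What to change.** In SAP 8.1.2:
- Replace the 1000 datasets with at least 10,000 relabelings per test. This brings the half-width at 0.05 to 0.0043 and the wrong-side chance at 0.045 or 0.055 to about 1%. Going further is optional: a half-width of 0.002 needs 45,618 relabelings.
- State that the empirical p-value is (b+1)/(m+1), where b is the number of relabelings at least as extreme as the observed result and m the total.
- Report the Monte Carlo 95% interval beside each empirical p-value.
- Prespecify the seed if it is not already given in text that is not visible, so that the result can be repeated.

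The cost is one number and a sentence or two in the SAP, plus somewhat longer run time. The model is small (about 128 subjects at most), so this should be slight, although run time in SAS, which the SAP specifies, was not tested. No data collection, visit or primary analysis changes.

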8.1.3. Subgroup Analyses of the Co-Primary Endpoints

[figure not shown]
Subgroup analyses by prior BoNT treatment experience, history of ULS due to stroke versus TBI, gender, and age will be performed for both co-primary efficacy endpoint with adjustments in the ANCOVA model for the ITT and populations. Descriptive statistics and the ANCOVA model will be run separately for each subgroup.

[figure not shown]
This document is confidential.

[figure not shown]
This document is confidential.

[figure not shown]
This document is confidential.

[figure not shown]
This document is confidential.

[figure not shown]
This document is confidential.

This document is confidential.

This document is confidential.

This document is confidential.

9. Safety

The safety population will be used for all safety analyses. Safety will be assessed on the basis of AEs, clinical laboratory values (hematology, INR, chemistry, and urinalysis), pregnancy test results, vital signs, [REDACTED] spirometry, and 12-lead electrocardiogram (ECG) results.

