3.1. Primary Objective

[figure not shown]
The primary objective of this study is to compare the safety and efficacy of a single treatment of DaxibotulinumtoxinA (DAXI) for injection at three dose levels (250 U, 375 U, 500 U) versus placebo in reducing muscle tone of adult subjects with upper limb spasticity (ULS) due to stroke or traumatic brain injury (TBI).

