3.4. Brief Description

This is a Phase 2, randomized, double-blind, placebo-controlled, parallel group, dose ranging, multi-center trial to evaluate the efficacy and safety of DAXI for injection in the treatment of ULS in adults after stroke or TBI. The trial will be conducted at approximately 30 sites across the United States.

Approximately 128 subjects with ULS will be randomly assigned

This document is confidential.

The co-primary efficacy endpoints are the mean change from baseline in muscle tone measured using the Modified Ashworth Scale (MAS) in the suprahypertonic muscle group (SMG) of the elbow, wrist, or finger flexors at Week 6 and the mean score on the Physician Global Impression of Change (PGIC) at Week 6.

- For subjects enrolled before COVID-19:
 - The end of study visit for a given subject can occur at Week 12 if the change in MAS score in the SMG is < 1-point reduction from baseline AND the PGIC score is ≤ 0 , OR
 - The end of study visit will occur after Week 12 when there is loss of muscle tone improvement in the SMG (i.e., a reduction from baseline in MAS score of < 1-point) AND the PGIC score is ≤ 0 . OR
 - Week 36 will be the end of study for all subjects, even those who maintain muscle tone improvement in the SMG (i.e., a reduction from baseline in MAS score of ≥ 1 point) OR PGIC score is ≥ 1 .
- For subjects enrolled after the COVID-19 20 March 2020 screening and randomization hold the end of study will be at Week 12.

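### Separate subgroup ANCOVAs, with no visible treatment-by-subgroup contrast, do not estimate whether effects differ, and the TBI fit may fail depending on unstated counts

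*SAP*

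**What the plan says.** SAP Section 8.1.3 names the factors: "Subgroup analyses by prior BoNT treatment experience, history of ULS due to stroke versus TBI, gender, and age". It applies them to both co-primary endpoints, mentions adjustments to the ANCOVA model without defining them, and then states: "Descriptive statistics and the ANCOVA model will be run separately for each subgroup".

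The model it points back to is in SAP Section 8.1.1. It has treatment, pooled center and prior BoNT treatment, plus baseline MAS for the MAS endpoint only. On centers, SAP Section 6.5 says: "Treatment centers with less than 4 subjects will be considered for pooling". A pooled center may hold at most 20 randomized subjects, and the final pooling is settled before database lock.

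The visible text of Section 8.1.3 contains no treatment-by-subgroup interaction, no minimum subgroup size and no fallback model. Neither document gives the expected share of TBI subjects or the final number of pooled centers.

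**The concern.** A subgroup analysis asks whether the treatment effect differs between levels of a factor. Separate fits answer a different question: whether the effect is detectable within each level. They give two estimates and two p-values, but no estimate or interval for the difference. When the levels are small, chance alone often makes one p-value significant and the other not, even if the effects are identical.

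With four factors, three doses and two endpoints there are 4 × 3 × 2 = 24 such pairs of p-values, if each factor has two levels. Protocol Section 3.5 looks to this trial for decisions on program development. An apparent difference between stroke and TBI, or between BoNT-naive and BoNT-experienced subjects, could steer those decisions without evidence behind it.

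The second worry is mechanical. A model with many center terms, refitted in a small subset such as TBI, may leave few or no residual degrees of freedom.

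**Working it through.** **Inputs from the SAP**

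- Size: "Approximately 128 subjects with ULS will be randomly assigned" (Section 3.4).
- Arms: four, from "at three dose levels (250 U, 375 U, 500 U) versus placebo" (Section 3.1).
- Testing: "All statistical tests will be 2-sided at the 0.05 significance level, unless otherwise indicated" (opening text of Section 8).
- Effect: "difference between an active treatment and the placebo arm of 0.9 to 1.1", with "a common standard deviation of 1.1" (Section 3.6).
- Sites: about 30 (Section 3.4; the protocol synopsis allows up to 35).

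**Assumptions, not in the visible text:** 1:1:1:1 allocation (32 per arm), the subgroup splits, a TBI share of 5% to 30%, and, for the simulations, half the subjects with prior BoNT and pooled centers of 4 to 20 subjects. PGIC could not be computed because no SD is visible.

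**1. The plan's own figure.** d = difference / SD: 0.9/1.1 = 0.82 and 1.1/1.1 = 1.00, which matches the stated 0.8 to 1.0. As a consistency check, n per arm = 2 × (1.96 + 1.2816)² × (1.1/0.9)² = 31.4, so 32 per arm and 128 in total at 90% power. The planned power is not visible, so this shows agreement only.

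**2. Discordant significance under identical effects, even split.** Each half has 16 per arm. The standard error is 1.1 × √(2/16) = 0.389.

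- Difference 0.9: power = Φ(0.9/0.389 − 1.96) = Φ(0.354) = 0.638. The chance that exactly one half is significant is 2 × 0.638 × 0.362 = 46%.
- Difference 1.1: power = Φ(0.868) = 0.807. The chance is 2 × 0.807 × 0.193 = 31%.

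For unequal splits with powers p and q the chance is p(1 − q) + q(1 − p). The same question was simulated with the Section 8.1.1 MAS model and 10 to 20 pooled centers (1,000 trials per cell):

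| Split | 0.9, no center terms | 1.1, no center terms | 0.9, center ANCOVA | 1.1, center ANCOVA |
|---|---|---|---|---|
| 50/50 | 46% | 31% | 48–50% | 41–44% |
| 30/70 | 54% | 42% | 58–62% | 54–64% |
| 20/80 | 63% | 56% | 71–72% | 72–81% |
| 10/90 | 74% | 74% | 78–84% | 82–91% |

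All rows are for 500 U versus placebo. The center-ANCOVA columns count only trials in which both models could be fitted. At 10/90 with 20 centers that was 6% of trials, so those entries are imprecise.

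**3. One model with an interaction.** In the same simulated trials, the 3-df treatment-by-subgroup test in all 128 subjects rejected in 3.8% to 7.2% of trials, near the nominal 5%. This is not a like-for-like comparison, since it tests all doses together, but it shows that a direct test of difference holds its error rate.

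**4. Precision of the direct contrast.** For one dose and an even split, without center terms, the interaction SE is 1.1 × √(2/16 + 2/16) = 0.55. The 95% interval is then about ±1.96 × 0.55 = ±1.08 MAS points.

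**5. TBI estimability.** With K pooled centers all represented, the MAS model has 1 (intercept) + 1 (baseline) + 3 (treatment) + 1 (prior BoNT) + (K − 1) = K + 5 parameters: 15 for K = 10, 25 for K = 20 and 35 for K = 30. If all centers were pooled, the cap of 20 would force at least 7 (128/20 = 6.4). A small subset will not contain every center, so estimability was simulated (600 trials per cell). Entries are the share of trials in which 500 U versus placebo is estimable with at least 1 residual df:

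| TBI subjects (share of 128) | K = 8 | K = 10 | K = 15 | K = 20 | K = 30 |
|---|---|---|---|---|---|
| 6 (5%) | 1% | 0% | 0% | 0% | 0% |
| 13 (10%) | 75% | 52% | 18% | 6% | 1% |
| 19 (15%) | 98% | 98% | 94% | 69% | 18% |
| 26 (20%) | 100% | 100% | 99% | 99% | 86% |
| 38 (30%) | 100% | 100% | 100% | 100% | 100% |

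Estimable does not mean informative. At 19 TBI subjects the median residual df across these columns is 7, 5, 3, 2 and 0.

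**The case against.** A reader might infer that the TBI model is likely to fail. The documents do not support that. They give no TBI share. Pooling below 4 subjects is only considered, and pooled centers may hold up to 20, so 20 center levels is one scenario among many. At 15% TBI the contrast is estimable in 69% or more of trials for up to 20 centers.

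Nor do the documents say that every subgroup fit keeps the full center model. Section 8.1.3 refers to adjustments, and a reduced model is an open reading. What stands is that the terms are not stated.

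A reader might also infer that the prior-BoNT subgroup models break down because that term is constant within each level. It is aliased with the intercept and leaves the treatment contrasts unchanged, so this is a wording point only.

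Text is missing from the public SAP. The sentence naming the analysis populations is broken, and the contents list goes from Section 8.1.3 on page 28 to Safety on page 36. An interaction test or a sparse-data rule could be there, so the point can be made only about the visible text.

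Finally, discordant p-values mislead only someone who reads them as differing effects, and the SAP does not propose that reading. The subgroup analyses also lie outside the protocol synopsis's six-step hierarchical procedure. Both remarks are fair and limit the consequence. They do not supply the missing contrast.

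**Conclusion.** The point holds in a limited form. As visible, Section 8.1.3 yields within-level results and no estimate of whether effects differ. With 1:1:1:1 allocation, an even split and identical true effects at d of 0.8 to 1.0, exactly one of the two levels is significant for 500 U versus placebo on MAS in about 31% to 50% of trials. The lower end is without center terms and the upper end with them. At d of about 0.8 a 30/70 split already gives 54% or more.

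Failure of the TBI model is a conditional risk. It is near certain at about 6 TBI subjects, depends strongly on the number of pooled centers at 13 to 19, and is uncommon at 26 or more, where the contrast is estimable in at least 86% of trials.

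The primary conclusion is unaffected. The change is worth making because it is cheap and because subgroup impressions from a dose-ranging trial may inform later design.

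**What to change.** For each subgroup factor and each co-primary endpoint, fit one ANCOVA in the full ITT set. Use the Section 8.1.1 terms for that endpoint (baseline MAS for the MAS endpoint only), and add the subgroup main effect and the treatment-by-subgroup interaction. For prior BoNT the main effect is already in the model. Report LS mean differences from placebo within each level with 95% confidence intervals, together with the interaction estimate. Label the results exploratory and do not interpret within-subgroup p-values. For levels too sparse to estimate, give descriptive statistics only. Replace the undefined adjustments with this list of terms.

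The cost is SAP wording and no new data. The number of models falls from at least 4 × 2 × 2 = 16 separate fits to 4 × 2 = 8. The downside is that center effects, covariate effects and residual variance are assumed common across subgroups. The interaction estimate will also be imprecise: by step 4 its interval is about as wide on each side as the whole targeted effect. A non-significant interaction must therefore not be read as evidence that the effects are equal.
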